9.6. Deviation from Analyses Planned in Protocol

Not applicable.

This document is confidential.

10. Pharmacodynamics

Samples collected for the assessment of ALXN1820 concentration will be retained and may be analyzed in the future.

Samples for measurement of serum total and free properdin concentrations, CAP activity, CCP activity, CLP (complement lectin pathway) activity and potentially other measures of complement activation as specified in Section 1.3 of the Protocol will be used for the PD analysis described in this SAP/section.

Serum samples will be collected as defined in Section 1.3 of the Protocol.

10.1.1. Endpoint(s)

- Change in serum concentrations of total and free properdin over time;
- Change in CAP activity using the Wieslab AP assay;
- Subgroup analysis of the PD parameters between healthy non-Japanese participants and participants of Japanese descent.

10.1.2. Analysis of the Endpoint

Pharmacodynamic analyses will be performed using the PD Set.

Missing concentration data for all participants who are administered scheduled study treatments will be considered as non-informative missing and will not be imputed. No concentration estimates will be provided for missing sample values.

For the serum concentrations, actual values, changes from baseline and percentages change from baseline will be summarized by time point for each treatment using the following descriptive statistics: number of participants, arithmetic mean, STD, CV, geometric mean, geometric CV, median, minimum, and maximum.

Mean (STD) serum concentration (change from baseline and percentage change from baseline) versus scheduled time profiles will be presented in figures.

Individual serum concentration (change from baseline and percentage change from baseline) versus scheduled time profiles will be presented similarly.

Serum concentrations, change from baseline and percentage change from baseline will be presented in a data listing by participant.

This document is confidential.

11. Safety

The population used for safety analyses will be the Safety Set (SS).

Safety analyses will include an analysis of all adverse events (AEs), Electrocardiograms (ECGs), clinical laboratory data, physical examinations, vital sign measurements and injection/infusion site evaluation measurements using descriptive statistics.

No inferential statistical analyses are planned on the safety parameters of this study.

11.1. Adverse Events

AEs for all participants in the Safety Set will be included in the AE summaries.

Adverse events will be summarized by SOC and PT for each cohort, study intervention within each cohort and overall, based on the MedDRA dictionary version 23.1.

If the relationship to study drug is missing for TEAEs, then the relationship will be counted as related to study product for the summary tables. Missing severity for TEAEs will be counted as Grade 3.

Treatment-emergent AEs are defined as AEs which commence on or after first study drug administration, or those that first occur before first study drug administration but worsen in frequency or severity after first study drug administration.

If the start date of an AE is partially or completely missing, the date will be compared as far as possible with the date of the start of administration of study drug. The AE will be assumed to be treatment-emergent if it cannot be definitively shown that the AE did not occur or increase in severity during the treatment period (worst case approach). The following general rules will be used:

- If the start day is missing but the start month and year are complete, an AE will not be considered as being treatment-emergent only if the start month/year is before the month/year of the first study drug administration;
- If the start day and month are missing but the start year is complete, an AE will not be considered as being treatment-emergent only if the start year is before the year of the first Study Drug administration;
- If the start date is completely missing, an AE will be considered treatment-emergent unless the stop date is before the first study drug administration.

Time since first/last dose will be calculated as the difference between the event start date/time and the date/time of the first/last dose prior to start. Time since first/last dose will be expressed in days, hours and minutes. If time is missing, duration will be calculated as the difference between the start date and dosing date plus 1 and expressed in days. Time since first/last dose and duration will only be calculated when both dates are complete.

Duration will be calculated for AEs that resolve as the difference between the resolution date and onset date plus 1 and expressed in days. Should an AE have a short duration (*i.e.* < 24 hours), the duration will be calculated as the difference between the resolution time and the onset time.

This document is confidential.

The summary tables will include the number of participants and the number of events. Percentages will be based on the number of participants. Repeat AE summary tables will be created to display percentages based on the number of events. For summaries by SOC and PT, a participant will be counted once at the SOC level and once at each PT within the SOC level.

For summaries by SOC, PT and maximum Common Terminology Criteria for Adverse Events (CTCAE) grading, a participant will be counted once at the highest CTCAE grading for which the event occurred at the SOC level and the highest CTCAE grading for each unique PT within that SOC level. Therefore, participants may only contribute once to each PT and once to each SOC level.

The summaries presenting frequency of AEs by SOC and PT will be ordered by overall descending frequency of SOC and then, within a SOC, by overall descending frequency of PT.

The following tables will be provided:

- An overall summary of the number and percentage of participants reporting TEAEs, serious TEAEs (TESAEs), TEAEs leading to death, TEAEs leading to withdrawal of study drug, TESAEs leading to withdrawal of study drug, TEAEs by relationship, TESAEs by relationship and TEAEs by CTCAE grade;
- TEAEs overall by system organ class and preferred term;
- TEAEs by maximum CTCAE grading, overall and by system organ class and preferred term;
- TEAEs by strongest relationship to study medication, overall and by system organ class and preferred term;
- TEAEs overall by system organ class;
- TEAEs overall by preferred term;
- Related TEAEs (TERAEs), overall by preferred term;
- TESAEs overall by system organ class and preferred term;
- TESAEs by maximum CTCAE grading, overall and by system organ class and preferred term;
- TESAEs by strongest relationship to study medication, overall and by system organ class and preferred term;

Only TEAEs (or TESAEs, as applicable) will be included in the summary tables, however we will generate separate listings for treatment-emergent and non-treatment-emergent AEs. Additional listings will be provided for deaths, serious adverse events, AEs resulting in withdrawal from the study and AEs resulting in study drug withdrawal.

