^k At Screening, supine and standing (orthostatic) blood pressures will be performed to exclude participants who are prone to orthostatic hypotension.

^l Predose triplicate 12-lead ECGs will be performed 3 times at approximately 2, 1, and 0.5 hours before the start of dosing.

- ^m A 24-hour Holter ECG will be performed up to 3 months prior to Day 1 to exclude pre-existing ECG abnormalities.
- ⁿ Planned randomization may be up to 7 days prior to dosing on Day 1.
- ^o Collection of post-dose PK/PD samples are to be collected from the non-infused arm and not the administration line in IV administered cohorts
- ^p Collection of blood (for serum, citrated and K2-EDTA, or Plasma P100 plasma) and urine.
- ^q Injection/infusion site reaction evaluation will continue until the reaction is fully resolved.
- ^r In case of any suspected case of hypersensitivity or anaphylaxis additional samples for the assessment of ADA may be collected at or near the time of the event.
- ^s The Investigator or qualified designee will meet with the participant at each visit to ensure they carry the clinical study participant safety card at all times and to review the potential meningococcal infection risks of ALXN1820, and to address any safety concerns of the participant.
- ^t Collection of adverse events and serious adverse events will begin after ICF signing.
- ^u Participants will be administered prophylactic antibiotic treatment, oral penicillin V 500 mg twice daily (equivalent to 1×10^6 units), beginning on the evening of Day -1 through Day 127, or until complement activity has normalized (as determined by CAP assay). If penicillin is not tolerated, second line antibiotics will be initiated at the discretion of the Investigator.

Abbreviations: ADA = antidrug antibody; BMI = body mass index; C5 = complement component 5; CAP = complement alternative pathway; CRU = clinical research unit; ECG = electrocardiogram; ELISA = enzyme-linked immunosorbent assay; EOI = end of infusion/injection; h = hour; HIV = human immunodeficiency virus; ICF = informed consent form; ID = identity; IEC = Independent Ethics Committee; IV = intravenous; K2-EDTA = dipotassium ethylenediaminetetraacetic acid; MCV4 = tetravalent meningococcal conjugate vaccine; min = minutes; OP = outpatient; PD = pharmacodynamic(s); PK = pharmacokinetic(s); SC = subcutaneous; SOI = start of infusion/injection; TB = tuberculosis; tx = treatment.

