8.3.1. Time Period and Frequency for Collecting AE and SAE Information

All AEs and SAEs will be collected from the signing of the ICF until the last follow-up visit.

All SAEs will be recorded and reported to Alexion or the designee immediately and under no circumstance should this exceed 24 hours, as indicated in Section 10.3 (Appendix 3). The Investigator will submit any updated SAE data to Alexion within 24 hours of it being available.

Investigators are not obligated to actively seek AE or SAE data after conclusion of the study participation. However, if the Investigator learns of any SAE, including a death, at any time after a participant has been discharged from the study, and he/she considers the event to be reasonably related to the study intervention or study participation, the Investigator must promptly notify Alexion.

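### SAP 11.1 contradicts itself on AEs with a partial start date: two of its three rules ignore a stop date known to precede first dose

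*SAP*

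**What the plan says.** SAP 11.1 gives a definition, a principle and three rules.

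- **Definition.** "Treatment-emergent AEs are defined as AEs which commence on or after first study drug administration", or those that begin earlier and worsen in frequency or severity after first dosing.
- **Principle for incomplete start dates.** The AE is assumed treatment-emergent "if it cannot be definitively shown that the AE did not occur or increase in severity during the treatment period (worst case approach").
- **Rule 1, day missing.** "an AE will not be considered as being treatment-emergent only if the start month/year is before the month/year of the first study drug administration".
- **Rule 2, day and month missing.** "an AE will not be considered as being treatment-emergent only if the start year is before the year of the first Study Drug administration".
- **Rule 3, no start date at all.** "If the start date is completely missing, an AE will be considered treatment-emergent unless the stop date is before the first study drug administration".

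On collection, Protocol 8.3.1 states: "All AEs and SAEs will be collected from the signing of the ICF until the last follow-up visit". The footnotes to the schedule of activities agree. The Protocol synopsis allows up to 79 days of screening, so pre-dose AEs will be in the database. SAP 11.1 also restricts the AE summary tables to TEAEs and treatment-emergent SAEs.

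**The concern.** A complete stop date before first dose settles the matter. The event neither began nor worsened after dosing, so it fails the definition and meets the principle's standard of proof. Rule 3 uses that evidence. Rules 1 and 2 do not, and their *only if* leaves no other ground for exclusion. A record with a known start month can therefore be classed wrongly, while the same record with no start date is classed correctly.

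TEAE incidence is part of the primary endpoint (SAP 5.1), and this classification decides which events reach the summary tables. Two other rules in SAP 11.1 add to the effect. A TEAE with missing relationship is counted as related, and one with missing severity as Grade 3, so a pre-dose event let in by Rule 1 or 2 could also appear as related or severe. In addition, two programmers could each follow the section faithfully and reach opposite answers on the same record.

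**Working it through.** The plan states no figure to reproduce. The check applies the rules to one record and then bounds the size.

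**1. One record, three levels of start-date information.** The dates are assumed: first dose 20 June, AE stopped 10 June.

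| Start date recorded | Rule | Literal result | Result under the principle |
|---|---|---|---|
| June, day missing | 1 | TEAE | not TEAE |
| Year only (dosing year) | 2 | TEAE | not TEAE |
| Nothing | 3 | not TEAE | not TEAE |

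If there is no stop date, or it is on or after 20 June, all three rules and the principle give TEAE. The conflict is confined to records with a stop date known to be before dosing.

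**2. How many pre-dose days are exposed.** Inputs: collection starts at consent (Protocol 8.3.1); screening lasts up to 79 days (Protocol synopsis). Assumptions: a full 79-day screening period, and Day 1 spread evenly over a 365-day year.

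- Rule 1: if Day 1 is day *d* of its month, then *d* − 1 pre-dose days share that month. The range is 1 − 1 = 0 to 31 − 1 = 30. The mean is 14.7 days, and 14.7/79 = 19% of screening.
- Rule 2: if Day 1 is day *k* of the year, the count is the smaller of *k* − 1 and 79, so the range is 0 to 79. The sum over the year is (0 + 1 + … + 78) + 79 × 286 = 3,081 + 22,594 = 25,675. The mean is 25,675/365 = 70.3 days, and 70.3/79 = 89% of screening.

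**3. Largest effect of one participant on incidence.** Inputs: 6 active and 2 placebo per cohort, up to 10 cohorts (SAP Table 1); pooled placebo and total active columns (SAP 7.1).

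- Active cohort: 1/6 = 16.7 percentage points.
- Pooled placebo, all ten cohorts: 1/20 = 5 points. If optional Cohort 7 is not opened: 1/18 = 5.6 points.
- All active, ten cohorts: 1/60 = 1.7 points.

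These are maxima. SAP 11.1 counts a participant once per SOC and once per PT, so a percentage moves only if that participant has no other TEAE in the category. Event counts, which SAP 11.1 also tabulates, rise by one in every case.

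**The case against.** **The principle already governs.** The three bullets are introduced as general rules under a sentence that would drop such an event, and the definition would drop it too. A careful programmer could exclude it on that basis. This stands to the extent that misclassification is not certain: the fault is a contradiction within the section. It does not remove the fault, because the bullets are the operational text and their *only if* points the other way.

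**Worst case is deliberate.** Over-counting is the conservative direction in a first-in-human study. But Rule 3 shows that the authors did not mean worst case to override a known pre-dose resolution.

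**The consequences are limited.** Safety analysis is descriptive, with no inference. AEs are monitored continuously, and treatment-emergent and other AEs are listed separately, so an affected record can be found. All of this stands.

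**Stronger readings that the documents do not support.**

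- A reader might infer that affected records are likely, because participants may be vaccinated during screening. For Rule 1 the timing hardly fits. The tetravalent vaccine and first serogroup B injection are due at least 56 days before Day 1, too early for an onset on the injection day to fall in the dosing month. A reaction beginning on the day of the serogroup B booster, given at its 28-day minimum, shares the dosing month only if Day 1 is the 29th, 30th or 31st: 11 + 11 + 7 = 29 of 365 dates, or 8%. Later onset raises this somewhat, and an earlier booster lowers it. Participants with adequate documentation need no study vaccination. Vaccine reactions are more relevant to Rule 2, but no rate of partial dates is given for either rule.
- A reader might also take Rule 2 to expose the whole pre-dose part of the calendar year. Collection from consent limits it to about 79 days.

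**Conclusion.** SAP 11.1 is inconsistent on this point. Its definition, its principle and Rule 3 make an AE with a known pre-dose stop date non-emergent; Rules 1 and 2, read literally, make it a TEAE when the partial start falls in the dosing month or dosing year. The missing stop-date test can only add TEAEs, never remove them.

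The size is bounded but not estimable: at most 16.7 points per affected participant in an active cohort and 5 points in pooled placebo at full enrollment, under the once-per-category condition. An affected record needs a partial start in the exposed window together with a known pre-dose stop, which should be uncommon. The 16.7- and 5-point figures should not be read as an expected bias. The 14.7-day and 70.3-day means rest on the full-length screening and evenly spread dosing dates assumed above.

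This is a minor point, worth correcting because it touches the primary endpoint and the remedy is short.

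**What to change.** Add one alternative condition to Rules 1 and 2 in SAP 11.1, so that an AE is also not treatment-emergent if:

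> *its stop date precedes the first dose of study drug; for a partial stop date, if the stop month/year (or the stop year, where only that is known) precedes that of first dosing.*

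Events stay treatment-emergent under these two rules if they have no stop date, a stop on or after first dosing, or a partial stop date in the dosing month/year (or dosing year if only the year is known). The worst-case approach is therefore kept wherever the timing is in doubt. Comparing a partial stop date month with month, or year with year, avoids setting a month against a full date.

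In the test record above, both conflicting results change to not TEAE and the Rule 3 result is unchanged. The cost is one clause in each of two bullets and about one line of derivation code. No data collection, table shell or sample size changes.

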11.2. Laboratory Evaluations

Safety laboratory samples for hematology, chemistry, urinalysis and coagulation will be collected at various different timepoints for different cohorts.

This document is confidential.

Samples for pregnancy test, alcohol breath test, urine drug screen, FSH, HIV (types 1 and 2) screen, hepatitis B and C screen will be collected.

Refer to Section 1.3 of the Protocol for the schedule of activities indicating when the respective samples are taken for each cohort.

The following parameters will be included:

Hematology: Platelet count, Red blood cell (RBC) count, Hemoglobin, Hematocrit, RBC indices (MCV, MCH, %reticulocytes), White blood cell (WBC) count with differential (neutrophils, lymphocytes, monocytes, eosinophils, basophils).

Clinical chemistry: Alanine aminotransferase (ALT)/serum glutamic-pyruvic transaminase (SGPT), Alkaline phosphatase, Aspartate aminotransferase (AST)/serum glutamic-oxaloacetic transaminase (SGOT), Blood urea nitrogen (optional), Calcium, Creatinine, Creatine kinase, Hemoglobin A1C, Potassium, Sodium, Serum albumin, Total and direct bilirubin, Total protein, Urea.

Urinalysis: Specific gravity, pH, glucose, protein, blood, ketones, bilirubin, urobilinogen, nitrite, leukocyte esterase by dipstick, Microscopic examination (if any leukocytes, more than a trace protein, nitrites, and blood [if not menstruating] are abnormal).

Coagulation: Prothrombin time, partial thromboplastin time, international normalized ratio.

Serology: Human immune deficiency virus (HIV)-1 and HIV-2 antibodies, hepatitis B surface antigen (HbsAg), anti-HBc + IgM (if IgG positive) and anti-hepatitis C virus with confirmation by hepatitis C virus Ribonucleic acid (RNA).

Serum human chorionic gonadotropin (hCG) pregnancy test (as needed for women of childbearing potential), Follicle-stimulating hormone estradiol (as needed in women of non-childbearing potential only).

Alcohol breath and urine drug screen: amphetamines, barbiturates, benzodiazepines, cocaine, opiates, phencyclidine, methamphetamine, 3,4-methylenedioxy-methamphetamine, methadone, and tetrahydrocannabinol [cannabinoids].

Other tests: Serum QuantiFERON®-TB test, Vaccine titer (meningococcal serogroups A, C, W135, and Y).

Laboratory parameter values will be graded according to the National Cancer Institute Common Terminology Criteria for Adverse Events (NCI CTCAE).

All summaries will be based on results in SI (standard international system of units) units and will be output in the order listed above.

Toxicity grading following the NCI CTCAE grades version 5.0 will also be derived for laboratory variables where applicable (see list below). Note, where gradings require investigator/clinical input, this will not be considered and only the numeric criteria will be used for the assignments. If this results in the criteria for more than one grade being met, the highest (worst) CTCAE grade will be assigned. For creatinine only, the criteria based on the upper limit of normal (ULN) will be used (changes compared to the baseline value will not be used), e.g., CTCAE defines Grade 1 as $> \text{ULN} - 1.5 \times \text{ULN}$ or $> 1 - 1.5 \times \text{baseline}$. Only the $\text{ULN} - 1.5 \times \text{ULN}$ criterion will be used (and not the baseline criterion).

This document is confidential.

The following parameters are CTCAE gradable:

- **Hematology:** Absolute neutrophil count (neutrophil), total leukocytes (Leukocytes), hemoglobin (only do the grading for Anemia, no grading for Hemoglobin increased), platelet count, Lymphocyte.
- **Coagulation:** International normalized ratio.
- **Chemistry:** Alanine aminotransferase albumin, alkaline phosphatase, aspartate aminotransferase, total bilirubin, creatinine, gamma-glutamyl transferase, glucose (only do the grading the Hypoglycemia, no grading for Hyperglycemia), creatine kinase.

Actual values and changes from baseline (screening) in hematology, coagulation, clinical chemistry, and urinalysis will be summarized by treatment.

Shift tables for hematology, clinical chemistry and coagulation from baseline CTCAE toxicity for each visit and to the maximum CTCAE grade on treatment for each parameter will be provided. Participants with both a non-missing baseline and at least one non-missing post-baseline grade will be included in the shift tables. Unscheduled data will be included in the worst case across all scheduled and unscheduled visits after the first dose of study treatment. This means that if there are CTCAE grades derived from both unscheduled and scheduled visits data per test per participant then the highest grade will be summarized.

For non-CTCAE gradable tests, a shift table will be provided showing shifts relative to the normal ranges. This summary of normal range category changes illustrates the number and percentage of participants who fall into specified categories (Decrease to Low, Change to Normal or No Change, Increase to High) by comparing the baseline normal range category to the planned time normal range category and the worst-case normal range category. The worst-case post-baseline row will be used to summarize the participants' overall worst-case normal range category change. The determination of the worst-case takes into account both planned and unscheduled assessments. Only laboratory tests which cannot be graded per CTCAE v. 5.0 specified criteria will be included.

Participants with missing baseline value are to be assumed to have normal baseline value. Worst-case can be either High or Low. If a participant has a Decrease to Low and an Increase to High during the same time interval, then the participant is counted in both the 'Decrease to Low' and 'Increase to High' categories. If a participant was high at baseline and decreases to Low during the time interval, then the participant is counted in the 'Decrease to Low' category. Likewise, if a participant was Low at baseline and increases to High during the time interval, then the participant is counted in the 'Increase to High' category. Participants are only counted in the 'Change to Normal or No Change' category if they are:

- Normal at baseline and have no normal range High and no normal range Low values during the time interval
 - High at baseline and do not change to Low during the time interval
 - Low at baseline and do not change to High during the time interval
- Shift tables by treatment will be produced for these laboratory parameters. These tables will summarize the number of participants

This document is confidential.

with each baseline grade relative to the reference ranges and changes to the worst highest grade assessed post-dose during the study.

All events of ALT $\geq 3 \times$ upper limit of normal (ULN) and bilirubin $\geq 2 \times$ ULN (> 35% direct bilirubin) which may indicate severe liver injury (possible Hy's Law), must be reported as an SAE. Optional outputs may be created if it is seen that ALXN1820 causes liver injury. For these optional outputs, liver function results will be presented in a summary table and eDISH (evaluation of drug-induced serious hepatotoxicity) plots.

All laboratory results, as well as CTCAE grades will be included in data listings. Abnormal results for hematology, clinical chemistry, urinalysis and coagulation will be listed separately. Laboratory results for serology, pregnancy and FSH, urine drug screen, alcohol breath test, QuantiFERON Tuberculosis test and MC4 Vaccine Titer will be listed only.

